6. ADVERSE EVENT AND SERIOUS ADVERSE EVENT REPORTING

6.1 DEFINITIONS

I. Adverse Event (AE)

An adverse event (AE) is any untoward medical occurrence in a subject that may present itself during the conduct of a research study and which may or may not have a causal relationship with the study procedures. An AE can therefore be any unfavorable or unintended sign (e.g., including an abnormal laboratory finding), symptom, or disease temporally associated with a study procedure. An AE may be a new illness, worsening of a sign or symptom of a condition, or an effect from a study procedure.

I. Serious Adverse Event (SAE)

A serious adverse event (SAE) is any untoward medical occurrence that:

a. Results in death.

- b. Is life-threatening, i.e., the subject was at immediate risk of death at the time of the event; it does not include any event which hypothetically might have caused death if it had occurred in a more severe form.
- c. Requires inpatient hospitalization or prolongation of existing hospitalization. Hospitalizations and/or surgical procedures that are scheduled to occur during the study period, for an illness or disease that existed before subject enrolment in the study, will not be considered AEs provided the pre-existing condition did not deteriorate (e.g., surgery performed earlier than the planned date).
- d. Results in persistent or significant disability or incapacity.

Medical and scientific judgment should be exercised in deciding whether expedited reporting is appropriate. In other situations, such as important medical events that may not be immediately life-threatening or result in death or hospitalization but may jeopardize the subject or may require intervention to prevent one of the other outcomes listed in the definition above. These should also usually be considered serious.

6.2 ATTRIBUTION

The relationship of the AE to study procedure will be assessed by the investigator to be not related, unlikely, possible, probable or definite, as follows:

a. Not related: No relationship between the AE and the study procedure, judged clearly and incontrovertibly due to extraneous causes such as concomitant medication(s) or the subject's clinical state.

- b. Unlikely: The AE is more likely due to an alternative explanation such as concomitant medication(s), concomitant disease(s) and/or the time relationship suggests that a causal relationship is unlikely.
- c. Possible: The AE might be due to a study procedure. An alternative explanation such as concomitant medication(s), concomitant disease(s) is inconclusive. The time relationship is reasonable therefore the causal relationship cannot be excluded.
- d. Probable: The AE might be due to a study procedure. An alternative explanation such as concomitant medication(s), concomitant disease(s) is less likely. The time relationship is suggestive, i.e. it is confirmed by dechallenge.
- e. Definite: The AE cannot be reasonably explained by an alternative explanation such as concomitant medication(s), concomitant disease(s). The time relationship is very suggestive, i.e. it is confirmed by dechallenge and re-challenge.

For the purposes of safety analyses, all SAEs classified with a relationship to a study procedure of possible, probable or definite will be considered study-related events.

6.3 PROCEDURES FOR AE AND SAE REPORTING AND MONITORING

All AEs experienced by the subject following signing of informed consent and any study procedure must be reported and recorded in the CRF. For both serious and non-serious AEs, the investigator must determine both the intensity of the event and the relationship of the event to study procedures.

All SAEs will be recorded in the CRF. The initial SAE report should include at a minimum: subject number, a narrative description of the event, and an assessment by the investigator of the intensity of the event and relationship of the event to study procedure. The initial SAE report should be complete as soon as possible. A complete follow-up SAE report must be submitted to DECBB when the information, not available at the time of the initial report, becomes available. The DECBB sponsor may request SAE follow-up information.

All AEs and SAEs should be monitored to determine the outcome or until the investigator consider it medically justifiable to terminate follow-up.

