5.3.2 LUMBAR PUNCTURE (OPTIONAL)

Should the participant give consent for obtaining CSF with lumbar puncture, another 1hour appointment would be made during the first visit and enrolment. Lumbar puncture will be done by a specialized physician at the hospital setting and will take approximately 60 minutes in total. Details of the procedures are as follows:

Patients must be lying in the lateral decubitus position on an examination or procedure bed, flexed, with the back horizontal and perpendicular to the bed throughout its entire length. It is important to ensure the patient is as flexed as possible, but shoulders should be perpendicular to bed, and knees and ankles should be symmetrically placed. Chorhexidine or iodine aqueous solution skin application will be applied around the site of puncture and continue in a concentric motion towards the iliac crest. Sterile drapes are placed to keep sterile conditions. CSF is collected from the

vertebral interspace L3-L4 as indicated by a line joining the tips of the iliac crests or L4-L5. Lidocaine 1% is administered subcutaneously. A lumbar puncture needed is inserted in the L3-4 or L4-5 interspace. Up to 10 mL of CSF will be collected. All tubes and polypropylene containers will be labeled with correct ID for the subject. CSF samples will be aliquoted into 0.5 ml polypropylene containers and then stored in a -80 fridge until they can be transported via cryoshipper to the DECBB at Robarts for permanent storage.

After the lumbar puncture is completed, participant will remain in the clinic for about 20 minutes for monitoring (so the visit will take 1 hour altogether). Participant will also be given something to eat and drink before leaving. Participant will be advised not to do any strenuous physical activity for the next 48 hours such as weight or other heavy lifting or straining. Study staff will call the participant day following the lumbar puncture to discuss how participant is feeling.

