5.4 STUDY FOLLOW UP

After the initial enrolment visit, study coordinator will follow up with phone calls periodically to confirm participants' decision to stay with the study; to verify contact information of the donor and their study partner, their primary care provider, residential or care facility staff and designated mortuary, if applicable. Participant will be provided a wallet-size enrollment card to sign and carry with them containing the DECBB contact info. They will receive information about how to contact site staff at the time of death. This will help the post-mortem arrangements to be carried out smoothly.

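### Section 6 uses drug-trial adverse-event wording that does not fit a biobank: collection has no end, expected death is not exempt, and the top relatedness grade cannot be reached

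*Protocol*

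**What the plan says.** **Collection.** Section 6.3: "All AEs experienced by the subject following signing of informed consent and any study procedure must be reported and recorded in the CRF". The only stopping rule there concerns an event already reported, which is monitored to its outcome or "until the investigator consider it medically justifiable to terminate follow-up". No last day is given for collecting new events.

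**Definition.** Section 6.1 covers any untoward occurrence during the study "which may or may not have a causal relationship with the study procedures". Its next sentence describes an AE as a sign, symptom or disease "temporally associated with a study procedure", with no window. It then counts new illness and worsening of a condition as AEs.

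**Seriousness.** An event is an SAE if it "Results in death". The one exemption in section 6 is for planned admissions or surgery for an illness that predates enrolment and has not worsened.

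**Attribution.** Section 6.2 describes the time relationship for *probable* as confirmed by dechallenge. For *definite*, "it is confirmed by dechallenge and re-challenge". SAEs graded possible, probable or definite are pooled as study-related.

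**Contacts.** Section 5.4: the "study coordinator will follow up with phone calls periodically to confirm" willingness to continue and to check contact details. The yearly contact in section 3.2(b) adds a change in clinical diagnosis. Section 5.3.2: "Study staff will call the participant day following the lumbar puncture to discuss how participant is feeling".

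**The concern.** Living donors register so that their brain can be donated after death (section 4.3.2). An open-ended AE rule in which every fatal event is serious therefore turns the event the bank is waiting for into a safety report. The routine contacts, meanwhile, are not set up to find the non-fatal complications that safety reporting is for, and the attribution scale borrows tests from drug trials, where treatment can be stopped and restarted.

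Three things are at stake: reporting work that tells nobody anything, a written rule that staff will not meet with the contacts described (although section 7 commits the study to following its protocol), and a complication record, chiefly for lumbar puncture, that is incompletely collected and awkwardly graded.

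**Working it through.** **1. The plan's own figure.** Section 4.1 projects 6-20 donations a year for 25 years, added to about 250 samples already stored, for a total of up to 750.

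- Upper rate: 250 + 25 × 20 = 750, which reproduces the stated figure.
- Lower rate: 250 + 25 × 6 = 400, consistent with a total given as a maximum.

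**2. Upper bound on fatal SAEs from donations.** Each new donation follows one death.

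- 25 × 6 = 150 and 25 × 20 = 500 over the horizon, or 6-20 a year. The highest rate is 20 / 12 = 1.7 a month.

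The AE rule can apply only to donors who consented while alive. Donors entered after death by a substitute decision maker (section 4.3.1) add none. The protocol does not give the split, so the share *s* registered while alive is an assumption. Fatal SAEs per year = *s* × (6 to 20); over 25 years, multiply by 25.

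| Assumed *s* | Per year | Over 25 years |
|---|---|---|
| 25% | 1.5-5 | 37.5-125 |
| 50% | 3-10 | 75-250 |
| 75% | 4.5-15 | 112.5-375 |
| 100% | 6-20 | 150-500 |

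Registered donors who die without donating would add to these counts; the protocol gives no figure for them.

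**3. Does the literal rule reach these deaths?** The blood draw belongs to enrolment (section 5.3.1), so consent and a study procedure are normally both in place from the start. Collection then has no end (6.3). Worsening of a condition is an AE, and one that is fatal is an SAE (6.1). The planned-admission exemption does not apply to death. On this reading the death is recorded, with narrative, intensity and relatedness (6.3).

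**4. Does another sentence say otherwise?** Yes. The sentence in 6.1 about a temporal link to a procedure would leave out a death years after a blood draw. But it sets no number of days, the sentence before it has no such limit, and 6.3 does not repeat it. The two sections give different answers for the same event and must be reconciled.

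**5. How would events be found?**

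| Event | Route in the protocol |
|---|---|
| During or just after lumbar puncture | About 20 minutes of monitoring in the clinic (5.3.2) |
| Next day after lumbar puncture | One call on how the participant feels (5.3.2) |
| After the blood draw visit | No dedicated contact |
| Later non-fatal events | Changed diagnosis at the yearly contact (3.2(b)); permission to see medical records (5.2, 5.3.1); no AE question listed |
| Death | Next of kin notifies staff (5.5) |

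Deaths have a firm route. Non-fatal events after the day-after call do not.

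**6. Can the relatedness grades be reached?** No repeat blood draw or puncture is scheduled, so re-challenge never happens and *definite* is closed as worded. *Probable* needs dechallenge only; for a procedure that is over once done, it is unclear what would count. *Possible* is unaffected. Because the study-related SAE category starts at *possible*, membership of that category does not change.

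**The case against.** The strongest reply is that the rule errs towards caution in a study with no treatment comparison and no safety endpoint. Every event gets a relatedness assessment. Section 6.2 sends events due to the subject's clinical state to the unrelated grade, and section 6.1 leaves expedited reporting to judgement. Even the upper bound is under two fatal reports a month. Estimating a complication rate is not among the objectives in section 2. All of this stands, and it limits the severity.

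Several stronger readings are tempting, and the documents do not support them:

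- *Every donor's death is beyond doubt an SAE.* The temporal-link sentence in 6.1 allows a narrower reading, and donors enrolled after death are outside the rule.
- *The calls never ask about events, so the rule cannot be met.* The day-after call asks how the participant feels, and the yearly contact can bring in a new illness. The case report form is not at hand, and the list in 5.4 is not said to be complete. What is shown is that the long-term contacts list no AE question.
- *Every hospitalization is an SAE.* Planned admissions for stable earlier illness are exempt. The cohort also includes healthy and previously concussed volunteers.
- *No procedure event can be graded above possible.* This is firm for *definite* but only arguable for *probable*.
- *Real complications are buried and no rate can be computed.* The pooling in 6.2 separates study-related SAEs from disease deaths. The weakness lies in finding later non-fatal events.

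What the reply does not remove is the conflict between 6.1 and 6.3, the missing end to collection, and a grade that the study's own procedures cannot satisfy.

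**Conclusion.** The point holds at moderate severity. Section 6 misfits the study's procedures in three ways: open-ended collection that conflicts with the temporal-link sentence and has no provision for expected death; no defined route for non-fatal events after the day-after call beyond a changed diagnosis or medical records; and a *definite* grade out of reach, with *probable* unclear.

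The size is at most 6-20 fatal SAEs a year from donations. This rests on the literal reading of 6.3, the projection in 4.1, and an assumed 100% of donors registered while alive. A reader might take 150-500 as the expected count. It is only an upper bound for donations, and it falls in proportion to the unstated share enrolled after death. Nor does the point call for a halt or put any analysis in doubt: there is no comparison to bias, and the pooled study-related SAE category is unchanged.

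**What to change.** Amend section 6 as follows.

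1. Reconcile 6.1 with 6.3 by tying AE and SAE collection to a stated window after each blood draw and each lumbar puncture, plus any later event judged to be procedure-related. The investigators should set the window length.
2. State that deaths and admissions from underlying disease outside the window are recorded as outcome data, not as SAEs.
3. Make the existing day-after-lumbar-puncture call record AEs explicitly, with a scripted question.
4. Define *probable* and *definite* by timing, site or mechanism, and absence of an alternative cause, without dechallenge or re-challenge.

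The cost is one protocol amendment with ethics approval (section 8.1) and one scripted question in a call already planned. It should remove more reporting than it adds. The downside is that unrelated events outside the window would no longer be logged as AEs.

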7. ETHICAL CONSIDERATIONS

The current study will be conducted in compliance with the protocol, International Conference on Harmonization Good Clinical Practice (ICH-GCP) and the applicable regulatory requirements. All staff including all delegated researchers will have undertaken GCP training. Copies of GCP training certificates will be held centrally.

7.1 INSTITUTIONAL REVIEW BOARD

All relevant documents for this study will be submitted to an appropriate Institutional Review Board (IRB) or Independent Ethics Committee (IEC) for review. A signed and dated letter documenting IRB/IEC approval must be obtained prior to entering subjects at the site. The IRB/IEC must be notified of all subsequent protocol amendments.

7.2 INFORMED CONSENT

Prior to any study procedures, it is the responsibility of the investigator to fully inform the subject, substitute decision maker or legally acceptable representative, of all pertinent aspects of the study. Each subject, substitute decision maker or a legally authorized representative must give written consent prior to the subject's participation in the study. The method of obtaining and documenting the informed consent and the contents of the consent must comply with ICH-GCP and all applicable regulatory requirement(s).

7.3 CONFIDENTIALITY OF SUBJECT RECORDS

The REDCap database system of Lawson will house the data. It will store data that has been processed to remove any direct identifiers of an individual study participant. Study subjects will be assigned a unique coded study identification number, which will be used to store their data in DECBB.

The investigator will grant monitor(s) and auditor(s) from regulatory health authorities' access to the subject's original medical records for verification of the data gathered and to audit the data collection process. The participant's confidentiality will be maintained and the participant's information will only be made publicly available to the extent permitted by the applicable laws and regulations.

In cases where participant identification is required, the recruiting site study investigator for the participant will be informed and be given access to only the minimum identifying information required to link the participant to the incidental finding and move it towards a resolution.

Data from this study that has had identifying information removed to the extent possible may be shared with researchers and organizations that are not part of this study. This open approach is being used by researchers internationally to better understand disease. Access to data by outside researchers or organizations will require a detailed plan for the use of the data, and approval from a research ethics board, as described in DECBB's Data Sharing Policy. These researchers or organizations will be required to enter into an agreement with DECBB that clearly states the safeguards that will be in place to protect the data, and the purposes for which this data may be collected, used, stored and disclosed.

DECBB may take some of the data and combine it with data from many other people, and make it available to enhance the public's awareness of research. Tools will be used to remove identifying information from these combined data sets, making the risk of identifying the participant negligible.

8. ADMINISTRATIVE REQUIREMENTS

8.1 PROTOCOL AMENDMENTS

The Sponsor may modify the protocol at any time during the life of the protocol. Protocol amendments will require IRB/IEC approval prior to implementation except when changes to the protocol are required to eliminate immediate hazards to the study subjects. The Sponsor and IRB/IEC must be notified immediately after such changes have occurred.

8.2 PREMATURE TERMINATION OF THE STUDY

If the investigator or Sponsor discovers sufficient reasonable cause for the premature termination of the study, the terminating party will provide written notification documenting the reason for study termination. The appropriate regulatory agencies and IRB/IEC must be notified.

8.3 ACCESS TO SOURCE DATA AND DOCUMENTS

The investigator will permit study related monitoring, audits, IRB/IEC review, and regulatory inspection(s), providing direct access to source data/documents.

8.4 RETENTION OF STUDY DOCUMENTS

The investigator must retain all study records for 25 years according to applicable regulatory requirements. If the investigator retires, relocates or withdraws from the responsibility of keeping the study records, custody must be transferred to a person willing to accept the responsibility. The regulatory bodies must be notified in writing if a custodial change occurs.

8.5 BIOLOGICAL SAMPLE AND DATA ACCESS POLICY

Biological samples will be stored at the Robarts Research Institute, Western University, London. The samples and clinical de-identified data will be available for investigators who wish to perform research. Access to these samples and data will be regulated by the Biological Sample & Data Access Committee which is made up of members from

DECBB. Requests for access will be assessed for feasibility, scientific rigor, and alignment with the consent of the participants. Samples will be shared with researchers both within Canada and Internationally. The full Biological Sample Access policy document is under development and will be made available upon its finalization.

8.5.1 DISTRIBUTION OF BRAIN BIOSPECIMENS AND TISSUES

All requests for brain and tissue specimens are to be placed through the application to the DECBB, available on the website (under development). Following review and approval by DECBB, staff coordinator will fill the request based on specimen availability. If questions arise, the requestor is contacted to clarify and confirm study design. Requestor's must follow the Tissue Request Instructions including the Tissue Request Guidelines and Tissue Request Standards when submitting a request.

DECBB end users are required to provide an account number with a shipping carrier to cover the costs of shipping the approved specimens. Shipping usually will occur between 4-6 weeks following approval; however, large requests may take longer to process. If the shipment is intended for a foreign country, the researcher is responsible for obtaining the required documents for entry of biohazardous material. Material and data transfer agreements required for such transfers will be completed between the Department of Pathology, LHSC and the requesting institution.

Points to be aware of or note in the request include,

- Clarification of amount of tissue or number of sections needed.
- b. Clarification of number of cases and unaffected controls requested.
- c. Method validation in postmortem human brain.

- d. Sample size required for pilot vs full study.
- e. Lack of availability of specific requested cases and the need for substitution

By accepting tissue from the DECBB, the researcher attests in the signed DMTA (data and material transfer agreement) to acknowledge in all publications and presentations DECBB as the source of tissue (e.g., "Human tissue was received from the DECBB at the Western University and the Lawson Health Research Institute"). Recipients are required to submit a summary progress report no later than 1 year after receipt of the tissues.

It is essential that individuals exercise universal precautions when handling samples from postmortem human subjects. All samples should be treated as if they are infected with bloodborne pathogens, even if evidence suggests otherwise (e.g., a subject is reported to be HIV negative). The materials received are experimental in nature and may have hazardous properties.

The provider makes no representations and extends no warranties of any kind, either expressed or implied. The recipient will use the material with all due skill and care and with dignity, sensitivity and respect. Unless prohibited by law, the recipient assumes all liability for claims for damages against it by third parties which may arise from the use, storage or disposal of the material except that, to the extent permitted by law, the provider will be liable to the recipient when the damage is caused by the gross negligence of willful misconduct of the provider.

